4.4 End of Study Definition

A subject is considered to have completed the study if he/she has completed all parts of the study, including the last visit Week 72 (EoS).

The EoS is defined as the date of the last visit of the last subject in the study globally.

5.0 STUDY POPULATION

Prospective approval of protocol deviations to recruitment and enrollment criteria, also known as protocol waivers or exemptions, is not permitted.

5.1 Inclusion Criteria

Subjects are eligible to be included in the study only if all of the following criteria apply:

- 1. Subjects should be 18 years or older at the time of signing the informed consent during the Screening visit.
- 2. Subjects with a chronic moderate to severe plaque-type psoriasis for at least 6 months (as determined by subject interview and confirmation of diagnosis through physical examination by Investigator).
- 3. Subjects must have moderate to severe nail psoriasis at Screening and Baseline, defined by:
 - mNAPSI score of ≥ 20 .
 - ViSENPsO ≥3
- 4. Subjects must have moderate to severe plaque psoriasis at Screening and Baseline, defined by:
 - s-PGA score of at least 3.
 - Body Surface Area (BSA) involvement of $\geq 10\%$.
 - PASI ≥12
- 5. Subjects must be considered candidates for systemic therapy, meaning psoriasis inadequately controlled by topical treatments (corticosteroids), and/or phototherapy, and/or previous systemic therapy.
- 6. Subjects have a negative evaluation for tuberculosis (TB) within 4 weeks before initiating study treatment, defined as a negative QuantiFERON® test. Subjects with a positive or 2 successive indeterminate QuantiFERON® tests are allowed if they have all of the following:
 - No history of active TB or symptoms of TB
 - A posteroanterior (PA) chest radiogram (with associated report available at study center) performed within 3 months of Screening with no evidence of active TB (or of any other pulmonary infectious diseases)
 - If prior latent TB infection (LTBI), must have a history of adequate prophylaxis (per local standard of care)
 - If the presence of LTBI is established, then treatment according to local country guidelines must have been followed for 4 weeks prior to inclusion in the study. A maximum of 2 QuantiFERON® tests are allowed. A re-test is only permitted if the first is indeterminate; the result of the second test will then be used.

- 7. Subjects are unlikely to conceive, as indicated by at least one "Yes" answer to the following questions:
 - Subject is a male
 - Subject is a female and agrees to abstain from heterosexual activity OR use a highly effective method of contraception as per Appendix 5.
 - Male subjects with female partners of childbearing potential who are not using birth control as described above must use a barrier method of contraception (e.g., condom) if not surgically sterile (i.e., vasectomy)
 - Subject is a surgically sterilized female or is documented to be postmenopausal. For contraceptive guidance, see Appendix 5.
- 8. For women of childbearing potential, a negative serum pregnancy test at Screening and a negative urine pregnancy test within 24 hours prior to Day 1 and on subsequent visits at which study treatment doses are scheduled.
- 9. Subjects must have results of a physical examination within normal limits or clinically acceptable limits to the Investigator prior to Day 1. The Investigator is encouraged to consult with the Medical Monitor (or appropriate designee) if there are questions regarding the significance of any out-of-range values.
- 10. Subjects must be capable of giving signed informed consent as described in Appendix 1, which includes compliance with the requirements and restrictions listed in the ICF and this protocol.

5.2 Exclusion Criteria

Subjects are excluded from the study if any of the following criteria apply:

- 1. Subjects who have laboratory abnormalities at Screening, including any of the following:
 - Alanine aminotransferase (ALT) or aspartate aminotransferase (AST) \geq 2.5 × the upper limit of normal (ULN).
 - Creatinine $\geq 2 \times$ the ULN.
 - Serum direct bilirubin ≥1.5 mg/dL.
 - White blood cell count $<3.0 \times 10^3/\mu L$.
 - Any other laboratory abnormality which, in the opinion of the Investigator, will prevent the subject from completing the study or will interfere with the interpretation of the study results.
- 2. Subjects who have predominantly non-plaque forms of psoriasis, specifically erythrodermic psoriasis, predominantly pustular psoriasis, medication-induced or medication-exacerbated psoriasis, or new-onset guttate psoriasis.

- 3. Subjects with ongoing inflammatory skin diseases other than psoriasis or any other disease affecting the fingernails, which may potentially confound the evaluation of the study treatment.
- 4. Subjects with fungal nail infection should be excluded from the study. Subjects in whom the Investigator suspects a fungal nail infection* (see Appendix 6) in addition to nail psoriasis should have scrapings sent for direct microscopy and fungal culture. If fungal culture or direct microscopy of nail scrapings turns out to be positive for fungal infection, the subject should be excluded from the study. At the discretion of the investigator, Periodic Acid-Schiff (PAS) staining for nail clippings could also be considered to rule out fungal infection of the nails. Direct microscopy or fungal culture is not required if fungal infection is diagnosed in PAS staining.
 - *Subjects with fungal nail infection whose fungal culture will be sent to the laboratory would have a Screening Period of 6 weeks.
- 5. Women of childbearing potential who are pregnant, intend to become pregnant (within 6 months of completing the study), or are lactating.
- 6. Subjects with any infection or history of recurrent infection requiring treatment with systemic antibiotics within 2 weeks prior to screening or severe infection (e.g., pneumonia, cellulitis, bone or joint infections) requiring hospitalization or treatment with intravenous (IV) antibiotics within 6 weeks prior to Screening.
- 7. Subjects with any previous use of tildrakizumab or other IL-23/Th-17 pathway inhibitors, including p40, p19, and IL-17 antagonists for psoriasis.
 - Prior use of TNF-alpha inhibitors with a wash-out period of 12 weeks would be allowed. However, the number of subjects with prior use of TNF-alpha inhibitors would be capped at 40%, and the analysis will be stratified based on prior use of these biologics.
- 8. Use of the medications listed below within the indicated washout period prior to Baseline visit:

Excluded Medications/treatments	Wash-out period prior to randomization
Topical psoriasis treatment (including medicated	2 Weeks
nail preparations)	
Conventional systemic psoriasis therapy (e.g.	4 Weeks
cyclosporine, methotrexate, acitretin, fumaric	
acid esters) or phototherapy (e.g. ultraviolet	
[UV] B light phototherapy, Psoralen-UVA	
(PUVA) therapy, tanning salon or home-	
administered UVB)	
Treatment with injectable or oral corticosteroids;	4 Weeks
Treatment with a biological agent other than	12 Weeks (or 5 half-lives, whichever is
Tildrakizumab or any other IL-23/Th-17	longer)
inhibitors, including p40, p19, or IL-17	
inhibitors	
Treatment with an investigational agent	4 Weeks (or 5 half-lives, whichever is
	longer)

- 9. Subjects with a positive human immunodeficiency virus test result, hepatitis B surface antigen, or hepatitis C virus test result. Subjects with Hepatitis C viral (HCV) antibody reactive test could be included if HCV-RNA is negative.
- 10. Subjects with a prior malignancy or concurrent malignancy (excluding successfully treated basal cell carcinoma, squamous cell carcinoma of the skin in situ, squamous cell carcinoma of the skin with no evidence of recurrence within 5 years or carcinoma in situ of the cervix that has been adequately treated).
- 11. Subjects who have received live viral or bacterial vaccination within 4 weeks prior to Baseline or who intend to receive live viral or bacterial vaccination during the study.
- 12. Subjects who are currently participating in another interventional clinical study or have participated in an interventional clinical study within 5 half-lives (of the drug) to wash out prior to randomization. (Subjects participating in observational studies or non-interventional registry studies may be included in the study).
- 13. Subject or family member is among the personnel of the study center or Sponsor/designee staff directly involved with this study.
- 14. Subjects who have any concomitant medical condition, which in the opinion of the Investigator, could affect the study outcome or present an unacceptable risk.
- 15. Subjects who were hospitalized due to an acute cardiovascular event (such as myocardial infarction, cerebrovascular accident, cardiovascular illness [e.g., angina pectoris], or cardiovascular surgery [such as coronary artery bypass]) within 6 months before Screening.
- 16. Subjects who, in the opinion of the Investigator, will not be reliable participants in the study and those who can confound the results of the study.
- 17. Subjects who have a history of alcohol or drug abuse in the previous year.
- 18. Subjects who have a high risk of suicidality at the Screening assessment based on the Investigator's judgment or, if appropriate, as indicated by a response of "yes" within the last 12 months to Questions 4 or 5 in the suicidal ideation section or any positive response in the behavioral section of the C-SSRS.
- 19. Subjects with any other clinically significant laboratory abnormality, which, in the opinion of the Investigator, will prevent the subject from completing the study or will interfere with the interpretation of the study results.
- 20. Subjects with a known history of allergy or hypersensitivity to any of the inactive ingredients of the Tildrakizumab or placebo formulations.

5.3 Lifestyle Considerations

Excessive exposure to sunlight should be avoided during the study. Subjects should avoid the use of tanning booths or other ultraviolet light sources for the duration of the study.

5.4 Screen Failures

Screen failures are defined as subjects who consent to participate in the clinical study but are not subsequently entered in the study. A minimal set of screen failure information is required to

ensure transparent reporting of screen failure subjects to meet the Consolidated Standards of Reporting Trials publishing requirements and to respond to queries from regulatory authorities. The minimal information includes demography, screen failure details, eligibility criteria, and any SAE.

Individuals who do not meet the criteria for participation in this study (screen failure) may be rescreened at the discretion of the Investigator for up to 2 additional times, with a minimum of 2 weeks between each rescreening. When a subject is rescreened, all Screening procedures will be repeated.

Note: If the original ICF was signed within 30 days of the rescreening visit, a new ICF does not need to be completed.

Rescreened subjects should not be assigned the same subject number as for the initial Screening. Any subject who is started on prophylactic treatment for latent TB during the Screening Period may be randomized 4 weeks after initiation of treatment without the need for rescreening. Any subject with a negative fungal nail infection whose fungal culture was sent to the laboratory would have a Screening Period of 6 weeks

6.0 STUDY TREATMENT

Study treatment is defined as any investigational treatment(s), marketed product(s), placebo, or medical device(s) intended to be administered to a subject according to the study protocol.

The study treatment in this study is tildrakizumab and placebo. All subjects will be dosed at the same time points to maintain the blind throughout the study. The study arms will receive study treatment during the course of the study as follows:

Arm A:

- o Tildrakizumab 100 mg SC injections at Weeks 0, 4, 16, 28, 40, and 52.
- Placebo injections at Weeks 32 and 44.

Arm B:

- o Placebo injections at Weeks 0, 4, 16, 40, and 52.
- o Tildrakizumab 100 mg SC injections at Weeks 28, 32, and 44.

6.1 Study Treatment Administered

Study treatment details are provided in Table 3.

Table 3: Study Treatment Details

Study Treatment Name:	Tildrakizumab	Placebo	
Dosage Formulation:	Tildrakizumab will be available as a prefilled syringe (PFS) with 100 mg of tildrakizumab and 1 mL solution. Each PFS will contain tildrakizumab solution and the following inactive ingredients: L-Histidine, L-Histidine Hydrochloride Monohydrate, Sucrose, and Polysorbate 80	The placebo formulation is similar to the tildrakizumab without the active ingredient. It will be available in PFS containing 1 mL solution and the following inactive ingredients: L-Histidine, L-Histidine Hydrochloride Monohydrate, Sucrose, and Polysorbate 80.	
Unit Dose Strength/Dosage Level:	100 mg	-	
Route of Administration	SC	SC	
Dosing Instructions:	All the subjects will be dosed at the same time points to maintain the study blinding throughout the study.		
For SC injections, tildrakizumab/placebo is supplied in a with a safety device. Each PFS is assembled with a safet accidental needle sticks. Subcutaneous injections should be rotated with each dos into moles, scars, tattoos, or areas where the skin is tend not intact. Abdominal administration is the preferred site for SC do		with a safety device to prevent with each dose and should not be given ne skin is tender, bruised, red, hard, or	
Packaging and Labeling	Tildrakizumab will be provided in PFS. Each PFS will be labeled as per country requirements.	Placebo will be available in identical containers with the same excipients (with no active drug)	

6.2 Preparation/Handling/Storage/Accountability

- 1) The Investigator or designee must confirm appropriate temperature conditions have been maintained during transit for all study treatments received, and any discrepancies are reported and resolved before the use of the study treatment.
- 2) Only subjects enrolled in the study may receive study treatment, and only authorized study center staff may supply or administer the study treatment. All study treatments must be stored in a secure, environmentally controlled, and monitored (manual or automated) area in accordance with the labeled storage conditions, with access limited to the Investigator and authorized study center staff.
- 3) The study treatment should be kept in a locked storage area under refrigerated storage at 2°C to 8°C. Study treatment experiencing temperature excursions outside this temperature should be quarantined and can only be released for subject use after consultation with the Sponsor.
- 4) The Investigator, institution, or the head of the medical institution (where applicable) is responsible for study treatment accountability, reconciliation, and record maintenance (i.e., receipt, reconciliation, and final disposition records).
- 5) Further guidance and information for the final disposition of unused study treatment will be provided by the study center monitor.

[figure not shown]
The Investigator, a member of the study center staff, or a hospital pharmacist must maintain an adequate record of the receipt and distribution of all study treatments using the Drug Accountability Form.

6.3 Measures to Minimize Bias: Randomization and Blinding

All subjects will be centrally assigned in a 1:1 ratio to receive either tildrakizumab 100 mg or a placebo using an Interactive Web Response System (IWRS). Before the study is initiated, the Login information and directions for the IWRS will be provided to each study center.

This is a double-blind study with limited access to the randomization code. Tildrakizumab and placebo will be identical in physical appearance. The treatment each subject will receive will not be disclosed to the Investigator, study center staff, subject, Sponsor, or study vendors. The treatment codes will be held by the Clinical Supplies Department of the Sponsor or their designated Contract Research Organization (CRO).

Study treatment will be dispensed at the study visits summarized in the SoA (see Section 1.3). All subjects will be dosed at the same time points to maintain the study blinding throughout the study. Returned study treatment should not be re-dispensed to the subjects.

6.4 Study Treatment Compliance

The prescribed dosage, timing, and mode of administration may not be changed. Any departures from the intended regimen must be recorded in the eCRFs.

On Week 0 (Day 1), Weeks 4, 16, 28, 32, 40, 44, and 52 the study treatment will be administered at the study center by appropriately trained staff.

Study treatment accountability and subject compliance will be documented throughout the treatment periods (Part 1 and Part 2) using study-specific study treatment dispensing record forms. If a subject does not receive the scheduled dose, every effort should be made to administer the dose as soon as possible.

6.5 Concomitant Therapy

Any medication or vaccine (including over-the-counter [OTC] or prescription medicines, vitamins, and/or herbal supplements) that the subject is receiving at the time of enrollment or receives during the study must be recorded on the eCRF along with:

- Reason for use.
- Dates of administration, including start and end dates.
- Dosage information, including dose and frequency.

In addition, all prior medications used to treat the disease conditions and any other medications taken within 6 months prior to enrollment must be recorded in the eCRF.

The Medical Monitor should be contacted if there are any questions regarding concomitant or prior therapy.

A list of excluded medications/therapy is provided in Table 4.

Other concomitant medication may be considered on a case-by-case basis by the Investigator in consultation with the Medical Monitor if required.

6.5.1 Rescue Medicine

Not applicable.

6.5.2 Allowed Concomitant Medication

- Acetaminophen (paracetamol) may be used by the subject as needed except within 7 days before a scheduled study efficacy evaluation except EOS/week 72 visit, when nail pain will be recorded on the NRS scale.
- Medications needed to treat pre-existing medical conditions that are not exclusionary to the study.
- Medications necessary to treat adverse events (AEs) or medical emergencies.
- Bland emollients (without α or β -hydroxy acids or keratolytic agents).
- Medicated shampoos that do not contain corticosteroids.
- Vitamins, supplements, antacids, and other over-the-counter medications that are not exclusionary to the study.
- Class VI or VII low-potency topical corticosteroids (such as prednicarbate 0.05%, triamcinolone acetonide 0.025%, fluocinolone acetonide 0.01%, desonide 0.05%, hydrocortisone 2.5% or hydrocortisone 1%) are allowed in Part 2 of the study, but not in Part 1.

Note that the use of any concomitant medication must relate to the documented medical history, prophylaxis, or an AE of the subject.

6.6 Dose Modification

No dose modification is allowed in this study. Study treatment can be interrupted temporarily or permanently if deemed necessary as per the Investigator's discretion.

6.7 Treatment after the End of the Study

The Sponsor will not provide any study treatment to the subjects during the Observational Safety Follow-up period. Patient care should not differ from what is normally expected for subjects with psoriasis.

6.8 Excluded Medication

Excluded medications/therapy is listed below. The concomitant use of an excluded medication/therapy with study treatment is not in compliance with the study protocol and must be recorded in the eCRF.

Table 4: Excluded Medications/treatments

Topical psoriasis treatment (including medicated nail preparations) *

Conventional systemic psoriasis therapy (e.g., cyclosporine, methotrexate, acitretin, fumaric acid esters) or phototherapy (e.g., ultraviolet [UV] B light phototherapy, Psoralen-UVA (PUVA) therapy, tanning salon or home-administered UVB)

Treatment with injectable or oral corticosteroids;

Treatment with a biological agent other than study treatment (including monoclonal antibodies, alefacept)

Treatment with an investigational agent (other than study treatment)

*Any class of topical corticosteroid is prohibited in the base study. Low-potency topical corticosteroids (class VI and VII) are only allowed during Part 2 of the study.

7.0 DISCONTINUATION OF STUDY TREATMENT AND SUBJECT DISCONTINUATION/WITHDRAWAL

7.1 Discontinuation of Study Treatment

Subjects may voluntarily discontinue study treatment for any reason at any time and enter the 20-week wash-out period or completely withdraw from the study (see Section 7.2). Subjects who consent to enter the wash-out period will undergo the Week 52 (EoT) assessment at approximately 4 weeks after administration of the last dose of study treatment.

At any time during Part 1 or Part 2 of the study, the Investigator should discontinue the study treatment of a given subject if, on balance, he/she believes that continuation would be detrimental to the subject's well-being.

The study treatment must be discontinued under the following circumstances, and the further steps need to be discussed with the Medical Monitor:

- An SAE, drug reaction or complication, or an unacceptable AE, whether attributed to study treatment or not, precludes the continuation of treatment with study treatment. This includes the development of allergic reactions or the development of other potentially serious drug reactions to medication required by the protocol.
- Diagnosis of malignancy (except basal or squamous cell carcinoma of the skin) during the study (at the discretion of the subject and Investigator).
- Meets early escape criteria at week 16 or week 28
- Subjects who develop suicidal behavior.
- Evidence of pregnancy.
- Withdrawal of informed consent.
- Lost to follow-up.
- Significant non-compliance of the subject with study procedures.
- Decision of the Sponsor to terminate the subject, study center, or the study.

Subjects who discontinue the study treatment may not be replaced.

Subjects who withdraw from the study will undergo the assessment that corresponds to the end assessment of the study part which they are leaving. Week 52 assessments (EoT) should be conducted approximately 4 weeks after administration of the last dose of study treatment.

See the SoA (see Section 1.3) for data to be collected at the time of treatment discontinuation and follow-up and for any further evaluations that need to be completed.

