Tildrakizumab is a high affinity (297 pM), humanized IgG1/K antibody that specifically binds to IL-23p19 (SN 08197) but does not bind human IL-12 (IL-12p40 and p35 heterodimer) or human p40. Tildrakizumab 100 mg by subcutaneous (SC) injection has recently been approved by the Food and Drug Administration for the treatment of moderate to severe chronic plaque psoriasis. Detailed information regarding the safety/tolerability of tildrakizumab can be found in the Investigator's Brochure (IB) (21).

Some special populations of patients will not be included in this study, such as those with hepatic, renal, and blood abnormalities, as well as infections, malignancy, myocardiopathy, and psychiatric disorders. Once we are evaluating a biological product to treat a nail condition, and based on the intrinsic characteristic of side effects that are generally observed in the class of biological products, we believe that these clinical conditions do not warrant the risk of generating or aggravating any of these clinical conditions, based on the following data:

- Liver function test elevations have been reported with the use of tumor necrosis factor inhibitors (TNF-I) in patients with rheumatoid arthritis receiving adalimumab, etanercept, or infliximab (22). The overall incidence of liver function test elevations >1x ULN with TNF-I use was uncommon, and abnormalities >2x ULN were rarely observed. Significant differences were most consistently observed with infliximab, less commonly with adalimumab, and were not observed with etanercept compared with comparator disease-modifying antirheumatic agents (DMARDs) (23).
- It is already described in the literature cases of vasculitis developed in association with the use of tumor necrosis factor-α (TNF-α) inhibitors. Although cutaneous small-vessel vasculitis was the most common finding, but systemic vasculitis, including peripheral nerve and renal vasculitis, was also frequently observed. (23, 24)
- Cases of drug-induced hemolytic anemia after treatment with infliximab and adalimumab for treating ulcerative colitis and psoriasis, respectively, were described. (25, 26)

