- An observational cohort study was conducted using medical and outpatient pharmacy claims from 2 large US health insurance claims databases from January 1, 2003, through September 30, 2015. The databases included 31,595 patients in the Optum Clinformatics Data Mart and 76,112 patients in Truven MarketScan who were new users of acitretin, adalimumab, apremilast, etanercept, infliximab, methotrexate, and ustekinumab. The pooled PS-matched analysis yielded a decreased rate of overall serious infection in users of apremilast (hazard ratio [HR], 0.50; 95% CI, 0.26-0.94), etanercept (HR, 0.75; 95% CI, 0.61-0.93), and ustekinumab (HR, 0.65; 95% CI, 0.47-0.89) compared with methotrexate. We did not find a different rate of overall serious infection among users of acitretin, adalimumab, and infliximab compared with methotrexate. (27)

- There is little research on the use of biologic treatment in psoriasis patients with a history of established malignancy (28). The existing evidence is not in all cases sufficient in order to provide adequate insight into the management of these complex situations (29); however, positive associations between cutaneous squamous cell carcinomas and certain therapies have been found, and there is conflicting evidence regarding the risk of lymphoma and melanoma. Further studies are needed to determine the long-term safety of newer psoriasis treatments (interleukin [IL]-12/23, IL-17, Janus kinase 1/3, and phosphodiesterase-4 inhibitors), specifically their safety in patients with a history of cancer (30).
- In a Korean, nationwide population-based prospective cohort study with a 15-year observational period. During the baseline period (1997-2000), total 1,773,786 Korean subjects who received health insurance from the National Health Insurance System were enrolled, and 5,788 subjects were defined as a psoriasis group. The number of newonset malignancies was collected during the observational period (2001-2015). Patients with psoriasis had a higher adjusted hazard ratio (aHR) for the development of overall malignancy (aHR 1.08, 95% confidence interval [CI] 1.00-1.18) and gastric cancer (aHR 1.31, 95% CI 1.08-1.58) compared to controls. The risks of non-Hodgkin lymphoma and non-melanoma skin cancer were significantly increased only in patients with psoriasis who received systemic treatments (aHR 2.86, 95% CI 1.07-7.61 and aHR 3.93, 95% CI 1.47-10.47, respectively) (31).

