To assess the effect of tildrakizumab on nail pain compared with placebo as measured by nail pain NRS score improvement at Week 28.	• The proportion of subjects with at least a 30% decrease in Nail Pain NRS score from Baseline at Week 28 in subjects with a baseline nail pain NRS score of > 3*.

EVELODATODY OD JECTIVES	EVDLODATODY ENDDOINTS
 EXPLORATORY OBJECTIVES To assess the effect of tildrakizumab over time 	• Change from Baseline in mNAPSI, NAPSI,
at measured time points through Week 52 as measured by mNAPSI, NAPSI, Nail Pain NRS, BSA, PGA-S, static Physician's Global	Nail Pain NRS, BSA, PGA-S, sPGA, PASI,
Assessment (s-PGA), PASI, To assess the effect of tildrakizumab on Quality of Life (QoL) as measured by: Dermatology Life Quality Index (DLQI) and Nail Assessment in Psoriasis and Psoriatic Arthritis QoL (NAPPA- QoL).	Change from Baseline in DLQI score (total and 6 domain scores) and NAPPA-QoL score at measured time points through Week 52.
 To assess the effect of tildrakizumab measured by using anchor scales: Clinician Global Impression of Change (CGIC) Clinician Global Impression of Severity (CGIS) Patient Global Impression of Change (PGIC). Patient Global Impression of Severity (PGIS). Patient Global Impression of Severity for pain (PGIS-P). Patient Global Impression of Change for pain (PGIC-P). 	Change from Baseline in CGIC, CGIS, PGIC, PGIC-P, PGIS, and PGIS-P at measured time points through Week 52.
SAFETY OBJECTIVE	SAFETY ENDPOINT
To assess the safety and tolerability of tildrakizumab in subjects with moderate to severe nail psoriasis over 52 weeks.	 The percentage of subjects with incidence, seriousness, and severity of all adverse events. The percentage of subjects with severe infections defined as any infection meeting the regulatory definition of a serious adverse event (SAE), or any infection requiring intravenous (IV) antibiotics, whether or not reported as a serious event as per the regulatory definition. The percentage of subjects with malignancies (excluding carcinoma in situ of the cervix). The percentage of subjects with non-melanoma skin cancer.

The percentage of subjects with melanoma
skin cancer.
The percentage of subjects with MACE.
The percentage of subjects with study
treatment-related hypersensitivity reactions
(e.g., anaphylaxis, urticaria, angioedema,
etc.).
The percentage of subjects with injection
site reactions (e.g. pain, erythema, edema
etc.).

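### Section 7.1 makes stopping for a new malignancy (other than basal or squamous cell skin carcinoma) both mandatory and discretionary, and nothing requires a hold or Medical Monitor agreement before the next dose

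*Protocol*

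**What the plan says.** Protocol Section 7.1 introduces its list with "The study treatment must be discontinued under the following circumstances, and the further steps need to be discussed with the Medical Monitor". The malignancy entry in that list is "Diagnosis of malignancy (except basal or squamous cell carcinoma of the skin) during the study (at the discretion of the subject and Investigator". It is the only entry whose own wording hands the decision to the subject and the Investigator.

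Other text that bears on the point:

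- **Section 7.1, general duty.** The Investigator should stop treatment "if, on balance, he/she believes that continuation would be detrimental" to the subject's well-being.
- **Section 7.1, other list entries.** An SAE or AE leads to a stop when it precludes further treatment. The list also contains "Decision of the Sponsor to terminate the subject, study center, or the study".
- **Section 7.1.1.** Treatment can be interrupted, for example for an intercurrent illness, major surgery or a Sponsor decision. The Medical Monitor should be informed, and restart can follow a discussion with the Monitor. Malignancy is not named.
- **Sections 8.3.1 and 8.3.6, Appendix 3.** Malignancy is an event of special interest, reported like an SAE: within 24 hours to the CRO, and from there to the Sponsor within at most 3 calendar days. No dosing action is attached.
- **Section 5.2, criterion 10.** Entry is barred for "Subjects with a prior malignancy or concurrent malignancy (excluding successfully treated basal cell carcinoma, squamous cell carcinoma of the skin in situ", with further exceptions that include adequately treated carcinoma in situ of the cervix.
- **Section 2.2.** On the conditions kept out of the study, malignancy among them, the protocol says "we believe that these clinical conditions do not warrant the risk of generating or aggravating any of these clinical conditions". It adds: "There is little research on the use of biologic treatment in psoriasis patients with a history of established malignancy".

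**The concern.** A stopping rule should tell a site what to do before the next injection. Here one site can stop a subject with a new cancer and another can give the next dose, and both can claim to follow Section 7.1. The second subject would stay on treatment with a condition that, outside the listed exceptions, would have barred entry.

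The crossover adds to this. Arm B receives its first active dose at Week 28 (Section 6.0), and subject and Investigator are blinded (Section 6.3). They would use their discretion without knowing whether the next dose continues the drug or starts it.

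What is at stake is subject safety and consistent conduct across sites, not the efficacy inference.

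**Working it through.** **Step 1: does any text require a hold, a stop or Medical Monitor agreement?**

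- *Section 7.1 list heading:* a Monitor step exists, but it is discussion rather than agreement. It concerns what follows a stop, so it is not clearly triggered when discretion is used to continue.
- *Section 7.1.1:* a hold-and-restart route exists, but it is optional, and its discussion applies only if dosing was interrupted.
- *Investigator's general duty, and the SAE entry:* both depend on case-by-case judgement.
- *Sponsor termination:* a power, not a rule.
- *Section 8.3.6:* reporting only.
- *Section 9.6:* a data monitoring committee may be set up; it need not be.

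None sets the rule. The protocol writes firm rules elsewhere. Under Section 8.2.3, suicidal behavior other than preparatory acts means a permanent stop. Under Section 8.3.5, pregnancy ends dosing.

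Malignancy is not the only entry that involves judgement: under Section 4.1.1, Week 16 early escape depends on selection by the Principal Investigator. That selection, however, is described outside the list.

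**Step 2: illustrative size.** The plan gives no figure to reproduce.

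Inputs:

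- Active doses (Section 6.0): Arm A at Weeks 0, 4, 16, 28, 40 and 52; Arm B at Weeks 28, 32 and 44.
- 48 subjects per arm (Section 9.2).
- Assumed, not from the documents: a constant rate *r* of 0.5 to 2 relevant malignancies per 100 subject-years, no dropout, 52 weeks = 1 year, and every affected subject continuing treatment.

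Subject-years up to the last active dose: 48 × 52/52 + 48 × 44/52 = 48 + 40.6 = 88.6. Expected events: 88.6 × 0.005 = 0.44 to 88.6 × 0.02 = 1.77.

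A dose at week *t* is at stake if the diagnosis falls in the *t* weeks before it. Expected doses at stake are therefore *n* × *r* × Σ*t*/52 in each arm.

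- Arm A: Σ*t* = 4 + 16 + 28 + 40 + 52 = 140, or 140/52 = 2.7 doses per event (at most 5).
- Arm B: Σ*t* = 28 + 32 + 44 = 104, or 104/44 = 2.4 doses per event (at most 3).
- Both arms: 48 × 244/52 = 225.2; × 0.005 = 1.1 and × 0.02 = 4.5 doses.

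If a sample size re-estimation took the study to its cap of 282 (141 per arm): 141 × 244/52 = 661.6, giving 3.3 to 13.2 doses.

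Part 1 only: 96 × 28/52 = 51.7 subject-years, giving 0.26 to 1.03 subjects.

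**Step 3: would reporting reach the Sponsor first?** The longest route is 1 + 3 = 4 days from the Investigator's awareness. Suppose awareness comes at diagnosis and diagnoses are spread evenly. The share falling within 4 days before an active dose is 5 × 4/364 = 5.5% in Arm A and 3 × 4/308 = 3.9% in Arm B; pooled, 32/672 = 4.8%. The report would usually arrive in time, but no text makes dosing wait for it.

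**The case against.** The strongest reply is that the heading governs. The stop is then compulsory and the closing clause is only loose wording. That reading is possible, but it leaves the clause with no function, and the remedy would be to delete it. On either reading the line needs correcting.

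A second reply is that the gap is narrow, and much of this stands. The Medical Monitor is named in the list heading and again in Section 7.1.1. All doses are given at the study center (Section 8.0), the subject may stop at any time, and the Investigator and the Sponsor can each stop treatment. A reader might infer that a new cancer is left without any oversight; the documents do not support that. What is missing is narrower: a required hold, and agreement before the next dose.

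A third reply is that an entry bar may properly be stricter than a stopping rule. Section 2.2 explains who is kept out, not what to do with subjects already treated, and the drug is approved at this dose for plaque psoriasis. This also stands. A reader might infer that the protocol's own reasoning demands an unconditional stop for every other malignancy. It does not: that choice is partly a clinical trade-off, and the discretion clause looks deliberate.

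**Conclusion.** The point holds as a minor one. Section 7.1 contradicts itself on a new malignancy other than basal or squamous cell skin carcinoma. Its natural reading permits continued dosing, and neither the Monitor discussion nor the hold in Section 7.1.1 closes that gap. The inconsistency is plain in the text. That dosing may continue rests on letting the specific clause prevail over the general heading.

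The dose counts are illustrative upper bounds, not a forecast. The assumed rate has no source in the documents. The doses would all be given only if no affected subject, Investigator or Sponsor stopped treatment. Dropout, for which the plan allows up to 10%, would lower the counts. The larger total at 282 subjects depends on a re-estimation that may not take place.

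Nor should a reader infer a threat to the primary result. At the highest assumed rate about one of 96 subjects would be affected by Week 28, which is not material to the primary analysis.

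**What to change.** In Section 7.1, replace the discretion clause with wording such as: *study treatment is held at diagnosis, and no further dose is given without documented Medical Monitor agreement.* This keeps individual judgement and tightens the route that Section 7.1.1 already offers. If the Sponsor intends a mandatory stop, delete the clause instead.

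In either case keep the basal and squamous cell skin exceptions and add adequately treated carcinoma in situ of the cervix. That agrees with exclusion criterion 10 and with the safety endpoint in Section 3.0, "The percentage of subjects with malignancies (excluding carcinoma in situ of the cervix".

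The cost is one line of text, with no change to data or analysis. It needs an amendment with IRB/IEC and, where applicable, regulatory approval (Appendix 1) at up to about 35 centers (Section 4.1), so it is best bundled with another amendment. An occasional subject would have a dose delayed or lost; if the hold became permanent, at most 5 active doses in Arm A or 3 in Arm B.
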